6.6.1. Dose Escalation and Stopping Rules

Precautionary sentinel dosing will be used in periods where escalating doses of PF-07328948 will be evaluated and may be omitted when repeating a dose level or administering a lower dose level than previously evaluated. Two participants (1 receiving PF-07328948 and 1 receiving placebo) within a period will be dosed initially before the remaining participants of that period are dosed. Safety and tolerability data through at least 24 hours post-dose for the sentinel participants will be reviewed prior to dosing the remaining participants of that period.

Dose escalation stopping rules will be used to determine whether the maximal tolerated dose has been attained. Dose escalation may be stopped if it is determined that the limits of safety and/or tolerability have been reached. This decision will be made after a discussion takes place between the sponsor study team and the investigator. The sponsor study team may not overrule the investigator's decision to stop dose escalation. If dose escalation is stopped because of any of these criteria, additional cohorts may receive the same or lower doses of the study intervention.

The dose escalation will be terminated based on the following criteria:

- If 50% or more of the participants receiving active drug at a given dose level (but not participants receiving placebo) develop similar clinically significant laboratory, ECG, or vital sign abnormalities, in the same organ class, indicating dose-limiting intolerance.
- Severe nonserious AEs, considered as, at least, possibly related to study intervention administration, in 2 participants at a given dose level (but not participants receiving placebo), independent of within or not within the same system organ class, indicating dose-limiting intolerance.
- Dosing will be paused for any SAE that occurs in a participant receiving active treatment until causality is fully assessed by the PI and sponsor. Dosing may resume if the SAE is determined to be not drug-related by the PI and sponsor. If the SAE is determined to be either drug-related or unknown, either dosing will cease or the SAE will be evaluated by the sponsor's protocol review committee (or similar review group), which is independent of the study team and investigators. If the protocol review committee determines that dosing may resume, a plan that mitigates risks to participants with the resumption of dosing will be implemented. Such a plan could

include a revision of inclusion/exclusion criteria, repeating or reducing the dose, or adding appropriate safety monitoring.

- It is determined that the limit of safety and/or tolerability has been reached. This decision will be made following discussions between the study team and the investigator.
- Other findings that, at the discretion of the study team and investigator, indicate that dose escalation should be halted.
- If, at any dose level, the average exposure reaches or exceeds the PK stopping limits: Unbound C_{max} of 285 ng/mL; or unbound AUC₂₄ of 3250 ng•h/mL.
- If, based on the observed data, the group mean $C_{max,u}$ or $AUC_{24,u}$ of the next planned dose is projected to exceed the escalation limits, that dose will not be explored. Modified doses may be explored if they are not expected to exceed PK stopping criteria.

Progression to the next dose level will occur if the last dose level is well tolerated and after satisfactory review of the available safety and PK data.

6.7. Continued Access to Study Intervention After the End of the Study

No study intervention will be provided to participants at the end of their study participation. It is expected that participants will be treated as required with standard-of-care treatments, as advised by their usual care physician.

6.8. Treatment of Overdose

For this study, any dose of PF-07328948 greater than 3000 mg within a 24-hour time period will be considered an overdose.

There is no specific treatment for an overdose.

In the event of an overdose, the investigator or treating physician should:

- 1. Contact the study medical monitor within 24 hours.
- 2. Closely monitor the participant for any AEs/SAEs and laboratory abnormalities as medically appropriate and at least until the next scheduled follow-up.
- 3. Document the quantity of the excess dose as well as the duration of the overdose in the CRF.
- 4. Overdose is reportable to Pfizer Safety only when associated with an SAE.

5. Obtain a blood sample for PK analysis within 3 days from the date of the last dose of study intervention if requested by the study medical monitor (determined on a case-by-case basis).

Decisions regarding dose interruptions or modifications will be made by the investigator in consultation with the study medical monitor as needed based on the clinical evaluation of the participant.

6.9. Prior and Concomitant Therapy

Use of prescription or nonprescription drugs and dietary and herbal supplements are prohibited within 7 days or 5 half-lives (whichever is longer) prior to the first dose of study intervention through the last PK collection, with the exception of moderate/strong CYP3A inducers or time-dependent inhibitors which are prohibited within 14 days plus 5 half-lives prior to the first dose of study intervention. Limited use of nonprescription medications that are not believed to affect participant safety or the overall results of the study may be permitted on a case-by-case basis following approval by the sponsor. Acetaminophen/paracetamol may be used at doses of ≤1 g/day.

Females taking hormone replacement therapy may be eligible to participate in this study if they are willing to discontinue therapy at least 28 days prior to the first dose of study treatment and remain off hormonal therapy for the duration of the study.

All concomitant treatments taken during the study must be recorded with indication, daily dose, and start and stop dates of administration. All participants will be questioned about concomitant treatment at each clinic visit.

Treatments taken within 28 days before the first dose of study intervention will be documented as a prior treatment. Treatments taken after the first dose of study intervention will be documented as concomitant treatments.

6.9.1. Rescue Medicine

There is no rescue therapy to reverse the AEs observed with PF-07328948; standard medical supportive care must be provided to manage the AEs.

7. DISCONTINUATION OF STUDY INTERVENTION AND PARTICIPANT DISCONTINUATION/WITHDRAWAL

7.1. Discontinuation of Study Intervention

It may be necessary for a participant to permanently discontinue study intervention. Reasons for permanent discontinuation of study intervention include the following: adverse events, or some other (administrative) reasons.

Note that discontinuation of study intervention does not represent withdrawal from the study. If study intervention is permanently discontinued, the participant should remain in the study to be evaluated for ongoing AEs. See the SoA for data to be collected at the time of

discontinuation of study intervention and follow-up for any further evaluations that need to be completed.

In the event of discontinuation of study intervention, it must be documented on the appropriate CRF/in the medical records whether the participant is discontinuing further receipt of study intervention or also from study procedures, posttreatment study follow-up, and/or future collection of additional information.

7.1.1. ECG Changes

A participant who meets either of the following bulleted criteria based on the average of triplicate ECG readings will be withdrawn from the study intervention.

- QTcF >500 ms.
- Change from baseline: QTcF >60 ms.

If a clinically significant finding is identified (including, but not limited to, changes from baseline in QTcF after enrollment), the investigator or qualified designee will determine if the participant can continue in the study and if any change in participant management is needed. This review of the ECG printed at the time of collection must be documented. Any new clinically relevant finding should be reported as an AE.

7.1.2. Potential Cases of Acute Kidney Injury

Participants exposed to study intervention demonstrating transient or sustained increase in SCr (with decrease in SCr-based eGFR or eCrCL) require expedited evaluation to differentiate AKI from DICI. DICI is defined as transporter-mediated effect related to altered renal tubular creatinine handling without histological injury.

Differentiating Acute Kidney Injury from Drug-Induced Creatinine Increase:

Both AKI and DICI are associated with

- confirmed Scr increase ≥0.3 mg/dL (≥26.5 μmol/L) within 48 hours

 OR
- confirmed Scr increase ≥ 1.5 times baseline (known or suspected to have occurred within the prior 7 days).

AKI is associated with

• simultaneous, confirmed SCys increase and confirmed Scr increase AND decrease in Scr-based eGFR and combined Scr-Scys-based eGFR (where applicable),

OR

• confirmed albuminuria increase

OR

• urine volume <0.5mL/kg/h for 6 consecutive hours.

DICI is associated with

• confirmed Scr increase without confirmed increase in reflex SCys

AND

• confirmed Scr-based eGFR decrease without confirmed combined Scr-Scys-based eGFR decrease (where applicable).

Confirmed post-baseline decrease in kidney function should be assessed individually based on clinical judgment. Cases wherein uncertainty remains, the investigator can review the case with the sponsor. Consult the Kidney Safety Council if such a situation occurs during the study for support if needed.

The participant should return to the site for evaluation as soon as possible, preferably within 48 hours of awareness of the abnormal results. Evaluation should include physical examination, laboratory tests, detailed medical and surgical history, review of all medications (including recreational drugs and supplements [herbal]), family history, sexual history, travel history, blood transfusion, and potential occupational exposure to chemicals. If appropriate, nephrology consultation may be recommended to facilitate differentiation of renal parenchymal disease, pre-renal azotemia, and post-renal obstruction. All confirmed cases of clinically relevant decrease in kidney function should be considered potential cases of DIKI if no other reason for the kidney function abnormalities has been found.

If ≥ 2 healthy participants in a given period/treatment arm are noted to have confirmed AKI, an assessment of whether the finding may be considered an adverse drug reaction should be undertaken.

7.1.3. COVID-19

If a participant has COVID-19 during the study, this should be reported as an AE or SAE (as appropriate) and appropriate medical intervention provided. Study treatment may continue unless the investigator/treating physician is concerned about the safety of the participant, in which case temporary or permanent discontinuation may be required.

It is recommended that the investigator discuss temporary or permanent discontinuation of study intervention with the study medical monitor.

7.2. Participant Discontinuation/Withdrawal From the Study

A participant may withdraw from the study at any time at their own request. Reasons for discontinuation from the study include the following:

- Refused further study procedure;
- Lost to follow-up;
- Death;
- Study terminated by sponsor;
- Discretion of the investigator or sponsor for safety or behavioral reasons, or the inability of the participant to comply with the protocol required schedule of study visits or procedures.

At the time of discontinuing from the study, if possible, an early discontinuation visit should be conducted. See the SoA for assessments to be collected at the time of study discontinuation and follow-up and for any further evaluations that need to be completed.

The early discontinuation visit applies only to participants who are enrolled/randomized and then are prematurely withdrawn from the study. Participants should be questioned regarding their reason for withdrawal.

The participant will be permanently discontinued from the study intervention and the study at that time.

If a participant withdraws from the study, they may request destruction of any remaining samples taken and not tested, and the investigator must document any such requests in the site study records and notify the sponsor accordingly.

If the participant withdraws from the study and also withdraws consent (see Section 7.2.1) for disclosure of future information, no further evaluations will be performed and no additional data will be collected. The sponsor may retain and continue to use any data collected before such withdrawal of consent.

7.2.1. Withdrawal of Consent

Participants who request to discontinue receipt of study intervention will remain in the study and must continue to be followed for protocol-specified follow-up procedures. The only exception to this is when a participant specifically withdraws consent for any further contact with them or persons previously authorized by the participant to provide this information. Participants should notify the investigator in writing of the decision to withdraw consent from future follow-up, whenever possible. The withdrawal of consent should be explained in detail in the medical records by the investigator, as to whether the withdrawal is only from further receipt of study intervention or also from study procedures and/or posttreatment study

follow-up, and entered on the appropriate CRF page. In the event that vital status (whether the participant is alive or dead) is being measured, publicly available information should be used to determine vital status only as appropriately directed in accordance with local law.

7.3. Lost to Follow-up

A participant will be considered lost to follow-up if the participant repeatedly fails to return for scheduled visits and is unable to be contacted by the study site.

The following actions must be taken if a participant fails to return to the clinic for a required study visit:

- The site must attempt to contact the participant and reschedule the missed visit as soon as possible. Counsel the participant on the importance of maintaining the assigned visit schedule and ascertain whether the participant wishes to and/or should continue in the study;
- Before a participant is deemed lost to follow-up, the investigator or designee must
 make every effort to regain contact with the participant (where possible, 3 telephone
 calls and, if necessary, a certified letter to the participant's last known mailing
 address or local equivalent methods). These contact attempts should be documented
 in the participant's medical record;
- Should the participant continue to be unreachable, the participant will be considered to have withdrawn from the study.

8. STUDY ASSESSMENTS AND PROCEDURES

8.1. Administrative Procedures

The investigator (or an appropriate delegate at the investigator site) must obtain a signed and dated ICD before performing any study-specific procedures.

Study procedures and their timing are summarized in the SoA. Protocol waivers or exemptions are not allowed.

Adherence to the study design requirements, including those specified in the SoA, is essential and required for study conduct.

All screening evaluations must be completed and reviewed to confirm that potential participants meet all eligibility criteria. The investigator will maintain a screening log to record details of all participants screened and to confirm eligibility or record reasons for screening failure, as applicable.

Participants will be screened within 28 days prior to administration of the study intervention to confirm that they meet the study population criteria for the study. If the time between screening and dosing exceeds 28 days as a result of unexpected delays (eg, delayed drug

shipment), then participants do not require rescreening if the laboratory results obtained prior to first dose administration meet eligibility criteria.

A participant who qualified for this protocol but did not enroll from an earlier cohort/group may be used in a subsequent cohort/group without rescreening, provided laboratory results obtained prior to the first dose administration meet eligibility criteria for this study. In addition, other clinical assessments or specimen collections, eg, retained research samples, may be used without repeat collection, as appropriate.

Every effort should be made to ensure that protocol-required tests and procedures are completed as described. However, it is anticipated that from time to time there may be circumstances outside the control of the investigator that make it unfeasible to perform the test. In these cases, the investigator must take all steps necessary to ensure the safety and well-being of the participant. When a protocol-required test cannot be performed, the investigator will document the reason for the missed test and any corrective and preventive actions that they have taken to ensure that required processes are adhered to as soon as possible. The study team must be informed of these incidents in a timely manner.

Any safety, laboratory, or analyte results that have been collected for the purposes of this study and could unblind the study will not be reported to investigative sites or other blinded personnel until the study has been unblinded.

If an IV catheter is utilized for blood sample collections, ECGs and vital sign assessments (pulse rate and BP) should be collected prior to the insertion of the catheter.

For samples being collected and shipped, detailed collection, processing, storage, and shipment instructions and contact information will be provided to the investigator site prior to initiation of the study.

The total blood sampling volume for individual participants in this study is approximately 515-550 mL. The actual collection times of blood sampling may change. Additional blood samples may be taken for safety assessments at times specified by Pfizer, provided the total volume taken during the study does not exceed 550 mL during any period of 56 consecutive days.

To prepare for study participation, participants will be instructed on the information in the Lifestyle Considerations and Prior and Concomitant Therapy sections of the protocol.

8.2. Efficacy Assessments

No efficacy assessments are being conducted in this study.

8.3. Safety Assessments

Planned time points for all safety assessments are provided in the SoA. Unscheduled safety measurements may be obtained at any time during the study to assess any perceived safety issues.

8.3.1. Physical Examinations

Physical examinations are to be performed at the nominal timepoints specified in the SoA. Additional physical examinations will be permitted, as necessary, to ensure appropriate collection of safety data.

A complete physical examination will include, at a minimum, head, ears, eyes, nose, mouth, skin, heart and lung examinations (including lung auscultation), lymph nodes, and gastrointestinal, musculoskeletal, and neurological systems.

A brief physical examination will include, at a minimum, assessments of general appearance, the respiratory (including lung auscultation) and cardiovascular systems, and participant-reported symptoms.

Physical examinations may be conducted by a physician, trained physician's assistant, or nurse practitioner as acceptable according to local regulation.

Height and weight will also be measured and recorded as per the SoA. For measuring weight, a scale with appropriate range and resolution is used and must be placed on a stable, flat surface. Participants must remove shoes, bulky layers of clothing, and jackets so that only light clothing remains. They must also remove the contents of their pockets and remain still during measurement of weight.

Physical examination findings collected during the study will be considered source data and will not be required to be reported, unless otherwise noted. Any untoward physical examination findings that are identified during the active collection period and meet the definition of an AE or SAE (Appendix 3) must be reported according to the processes in Sections 8.4.1 to 8.4.3.

8.3.2. Neurological Examinations

Neurological examinations as part of the physical exam may be conducted by a physician, trained physician's assistant, or nurse practitioner as acceptable according to local regulation. The neurological exam will consist of assessment of higher cortical function, the cranial nerves, motor function, deep tendon reflexes, sensory exam, and coordination and gait. The exam should be done to the extent needed to assess the participant for any potential changes in neurological status, as determined by the investigator (or designee).

8.3.3. Vital Signs

8.3.3.1. Blood Pressure and Pulse Rate

Supine BP will be measured with the participant's arm supported at the level of the heart, and recorded to the nearest mm Hg after approximately 5 minutes of rest. The same arm (preferably the dominant arm) will be used throughout the study. Participants should be instructed not to speak during measurements. When triplicate measurements of supine BP or pulse rate are required per SoA, measurements should be collected 2-4 minutes apart.

The same properly sized and calibrated BP cuff will be used to measure BP each time. The use of an automated device for measuring BP and pulse rate is acceptable; however, when done manually, pulse rate will be measured in the brachial/radial artery for at least 30 seconds. When the timing of these measurements coincides with a blood collection, BP and pulse rate should be obtained prior to the nominal time of the blood collection.

8.3.3.2. Respiratory Rate

Respiratory rate will be measured after approximately 5 minutes rest in supine position by observing and counting the respirations of the participant for 30 seconds and multiplied by 2. When blood pressure is to be taken at the same time, respiration measurement will be done during the 5 minutes of rest and before blood pressure measurement.

Additional collection times, or changes to collection times, of vital signs will be permitted, as necessary, to ensure appropriate collection of safety data.

Any untoward vital sign findings that are identified during the active collection period and meet the definition of an AE or SAE (Appendix 3) must be reported according to the processes in Sections 8.4.1 to 8.4.3.

8.3.4. Electrocardiograms

Standard 12-lead ECGs utilizing limb leads (with a 10-second rhythm strip) should be collected at times specified in the SoA section of this protocol using an ECG machine that automatically calculates the HR and measures PR interval, QT interval, QTcF, and QRS complex. Alternative lead placement methodology using torso leads (eg, Mason-Likar) should not be used given the potential risk of discrepancies with ECGs acquired using standard limb lead placement. All scheduled ECGs should be performed after the participant has rested quietly for at least 5 minutes in a supine position.

Triplicate 12-lead ECGs will be obtained approximately 2-4 minutes apart; the average of the triplicate ECG measurements collected at -1.0, -0.5, and 0 hours pre-dose on Day 1 of each period will serve as each participant's baseline QTcF value for that period.

To ensure safety of the participants, a qualified individual at the investigator site will make comparisons to baseline measurements. Additional ECG monitoring will occur if a) the mean value from the triplicate measurements for any postdose QTcF interval is increased by ≥60 ms from the baseline and is >450 ms; or b) an absolute QT value is ≥500 ms for any scheduled ECG. If either of these conditions occurs, then a single ECG measurement must be repeated at least hourly until QTcF values from 2 successive ECGs fall below the threshold value that triggered the repeat measurement.

For single ECG collections, additional ECG monitoring will occur if a) a postdose QTcF interval is increased by ≥60 ms from the baseline **and** is >450 ms; or b) an absolute QT value is ≥500 ms for any scheduled ECG. If either of these conditions occurs, then 2 additional ECGs will be collected approximately 2 -4 minutes apart to confirm the original measurement. If the QTcF values from these repeated ECGs remain above the threshold

value, then a single ECG must be repeated at least hourly until QTc values from 2 successive ECGs fall below the threshold value that triggered the repeat measurement.

If a) a postdose QTcF interval remains ≥60 ms from the baseline and is >450 ms; or b) an absolute QT value is ≥500 ms for any scheduled ECG for greater than 4 hours (or sooner, at the discretion of the investigator); or c) QTcF value get progressively longer, the participant should undergo continuous ECG monitoring. A cardiologist should be consulted if QTcF values do not return to less than the criteria listed above after 8 hours of monitoring (or sooner, at the discretion of the investigator).

In some cases, it may be appropriate to repeat abnormal ECGs to rule out improper lead placement as contributing to the ECG abnormality. It is important that leads be placed in the same positions each time in order to achieve precise ECG recordings. If a machine-read QTcF value is prolonged, as defined above, repeat measurements may not be necessary if a qualified medical provider's interpretation determines that the QTcF values are in the acceptable range.

ECG values of potential clinical concern are listed in Appendix 8.

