8.4.3. Follow-Up of AEs and SAEs

After the initial AE or SAE report, the investigator is required to proactively follow each participant at subsequent visits/contacts. For each event, the investigator must pursue and obtain adequate information until resolution, stabilization, the event is otherwise explained, or the participant is lost to follow-up (as defined in Section 7.3).

In general, follow-up information will include a description of the event in sufficient detail to allow for a complete medical assessment of the case and independent determination of possible causality. Any information relevant to the event, such as concomitant medications and illnesses, must be provided. In the case of a participant death, a summary of available autopsy findings must be submitted as soon as possible to Pfizer Safety.

Further information on follow-up procedures is provided in Appendix 3.

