10.8. Appendix 8: ECG Findings of Potential Clinical Concern

ECG Findings That May Qualify as AEs

- Marked sinus bradycardia (rate <40 bpm) lasting minutes.
- New PR interval prolongation >280 ms.
- New prolongation of QTcF to >480 ms (absolute) or by ≥ 60 ms from baseline.
- New-onset atrial flutter or fibrillation, with controlled ventricular response rate: ie, rate <120 bpm.
- New-onset type I second-degree (Wenckebach) AV block of >30 seconds' duration.
- Frequent PVCs, triplets, or short intervals (<30 seconds) of consecutive ventricular complexes.

ECG Findings That May Qualify as SAEs

- QTcF prolongation >500 ms.
- New ST-T changes suggestive of myocardial ischemia.
- New-onset LBBB (QRS complex>120 ms).
- New-onset right bundle branch block (QRS complex>120 ms).
- Symptomatic bradycardia.
- Asystole:
 - In awake, symptom-free participants in sinus rhythm, with documented periods of asystole ≥3.0 seconds or any escape rate <40 bpm, or with an escape rhythm that is below the AV node.
 - In awake, symptom-free participants with atrial fibrillation and bradycardia with 1 or more pauses of at least 5 seconds or longer.
 - Atrial flutter or fibrillation, with rapid ventricular response rate: rapid = rate >120 bpm.
- Sustained supraventricular tachycardia (rate >120 bpm) ("sustained" = short duration with relevant symptoms or lasting >1 minute).

- Ventricular rhythms >30 seconds' duration, including idioventricular rhythm (HR <40 bpm), accelerated idioventricular rhythm (HR >40 bpm to <100 bpm), and monomorphic/polymorphic ventricular tachycardia (HR >100 bpm [such as torsades de pointes]).
- Type II second-degree (Mobitz II) AV block.
- Complete (third-degree) heart block.

ECG Findings That Qualify as SAEs

- Change in pattern suggestive of new myocardial infarction.
- Sustained ventricular tachyarrhythmias (>30 seconds' duration).
- Second- or third-degree AV block requiring pacemaker placement.
- Asystolic pauses requiring pacemaker placement.
- Atrial flutter or fibrillation with rapid ventricular response requiring cardioversion.
- Ventricular fibrillation/flutter.
- At the discretion of the investigator, any arrhythmia classified as an adverse experience.

The enumerated list of major events of potential clinical concern are recommended as "alerts" or notifications from the core ECG laboratory to the investigator and Pfizer study team, and not to be considered as all-inclusive of what to be reported as AEs/SAEs.

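### Protocol 8.3.4 puts its absolute 500 ms repeat-ECG trigger on uncorrected QT, so a narrow band of mean QTcF above 500 ms requires withdrawal but meets no repeat-ECG trigger

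*Protocol*

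**What the plan says.** Section 8.3.4 has the ECG machine report QT and QTcF as separate quantities. For triplicate collections it gives two triggers for additional monitoring: (a) mean post-dose QTcF at least 60 ms above baseline and above 450 ms; or (b) "an absolute QT value is ≥500 ms for any scheduled ECG". Trigger (b) appears again, still on QT, in the single-ECG paragraph and in the continuous-monitoring paragraph, where it must last more than 4 hours.

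The rules around it use the corrected interval:

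- Triplicate exit (8.3.4): ECGs at least hourly "until QTcF values from 2 successive ECGs fall below the threshold value that triggered the repeat measurement".
- Single ECGs (8.3.4): confirmation is judged on QTcF from two further tracings, then hourly ECGs "until QTc values from 2 successive ECGs fall below the threshold value that triggered the repeat measurement".
- Continuous monitoring (8.3.4): a further trigger (c) applies if QTcF lengthens progressively, and after 8 hours of monitoring "A cardiologist should be consulted if QTcF values do not return to less than the criteria listed above".
- Withdrawal (7.1.1): the criteria are QTcF above 500 ms or a rise above 60 ms; a participant meeting either "based on the average of triplicate ECG readings will be withdrawn from the study intervention".
- Appendix 8: "QTcF prolongation >500 ms" is among the findings that may qualify as an SAE.

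**The concern.** QT and QTcF agree only at 60 bpm. Above that rate QT is shorter than QTcF, so a 500 ms limit on QT is reached later than the same limit on QTcF. A participant can therefore have a mean QTcF that the protocol treats as reason to stop dosing, without the repeat-ECG rule applying.

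This matters because each period is a single dose. When the finding appears, the dose has already been taken. Withdrawal prevents the next dose, but only monitoring addresses the current one. The exit rule has the reverse problem at low heart rates: it compares QTcF with a threshold that was crossed by QT.

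**Working it through.** There is no plan figure to reproduce. The check applies the stated thresholds jointly.

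**Inputs**

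- Fridericia formula (SAP 3.5.4): QTcF = QT / (60/HR)^(1/3), so QT = QTcF × (60/HR)^(1/3).
- Trigger (a): rise ≥60 ms and QTcF >450 ms. Trigger (b): QT ≥500 ms (Protocol 8.3.4).
- Withdrawal: mean QTcF >500 ms, or rise >60 ms (Protocol 7.1.1).
- Eligibility limit: QTcF 450 ms at screening (Protocol 5.2). Assumption: the period baseline is also at most 450 ms. The documents do not restate the limit for each period.

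**Step 1: missing (a).** With QTcF >500 ms, (a) is missed only if the rise is below 60 ms. Baseline must then exceed 500 − 60 = 440 ms. In whole milliseconds, QTcF 501 needs a baseline of at least 501 − 59 = 442. With a baseline of at most 450, the highest QTcF missing (a) is 450 + 59 = 509.

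**Step 2: missing (b).** QT <500 ms requires HR > 60 × (QTcF/500)^3.

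| Mean QTcF (ms) | Baselines missing (a) (ms) | HR above which QT <500 ms (bpm) |
|---|---|---|
| 501 | 442–450 | 60.4 |
| 505 | 446–450 | 61.8 |
| 509 | 450 | 63.3 |

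At 510 ms from a baseline of 450 ms the rise is 60 ms and (a) is met. If a period baseline were above 450 ms, the upper end would move up 1 ms per ms; at 455 ms the band is 501 to 514 ms.

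**Step 3: example.** Baseline 448, post-dose mean 505 (rise 57 ms), HR 75: QT = 505 × (60/75)^(1/3) = 468.8 ms. Section 7.1.1 requires withdrawal, and neither trigger is met. Trigger (b) can be read against any individual tracing, but that tracing would need a QT 500 − 468.8 = 31.2 ms above this mean.

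**Step 4: grid check.** Over whole-ms baselines 360–450 and post-dose values 400–560, the number of pairs with QTcF >500 ms meeting neither trigger is 0 at HR 50, 55 and 60; 17 at HR 61; 35 at HR 62; 44 at HR 63; and 45 at each of HR 64, 65, 70, 75 and 80. These are counts of cells, not likelihoods.

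**Step 5: the exit rule at low heart rate.** QT 500 ms corresponds to QTcF 470.5 ms at HR 50 and 485.7 ms at HR 55. Trigger (b) then fires with QTcF already below 500 ms, so a QTcF exit at 500 ms is satisfied even if QT has not moved.

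**Step 6: candidate wordings.** With (b) on QT or QTcF ≥500 ms, the Step 4 count is 0 at every heart rate checked and no existing trigger is lost. Replacing QT by QTcF also gives 0, but loses 725 pairs at HR 50 (QTcF 471–499) and 245 at HR 55 (QTcF 486–499) that now trigger.

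**Step 7: when it matters.** Tables 1 and 2 of the protocol schedule ECGs at 1, 2, 3, 4, 8, 12, 24, 48 and 72 h, with telemetry to 8 h. A finding first seen at 8 h or later could wait 4 to 24 h for the next scheduled ECG.

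**The case against.** The strongest reply is that this is a terminology slip that sites would read through. The exit rule compares QTcF with the triggering threshold, a later sentence in 8.3.4 speaks of prolonged QTcF as if already defined, and the screening rule in 5.2 tells sites to correct a long QT and decide on QTcF. That stands as the likely explanation. It does not remove the literal text, which states QT three times in a section that distinguishes the two intervals.

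The second reply is that other provisions cover the participant:

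- Section 7.1.1 requires a documented management review of clinically significant QTcF changes.
- Trigger (c) leads to continuous monitoring if QTcF lengthens progressively.
- Section 8.3 says "Unscheduled safety measurements may be obtained at any time during the study".
- For a reported event, Section 8.4.3 says "the investigator must pursue and obtain adequate information until resolution, stabilization", and Section 10.3.3 adds supplemental measurements as medically indicated.
- The early-termination column of Table 1 includes a 12-lead ECG, which arguably applies after withdrawal.
- Participants in the remaining cohorts are confined to 72 h.

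These reduce the consequence considerably, and following a QTcF of 505 ms without another ECG would be unusual practice. Each is discretionary, conditional or not tied to a time, however, and none requires repeat ECGs because QTcF exceeds 500 ms.

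Third, nothing says that every withdrawal under 7.1.1 must also meet an 8.3.4 trigger. That is correct: trigger (a) deliberately adds a 450 ms floor that 7.1.1 lacks. The point here is confined to an absolute limit of the same size expressed in two different intervals.

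**Conclusion.** The mismatch is real and minor. A mean QTcF above 500 ms, less than 60 ms above a baseline that itself exceeds 440 ms, at a heart rate above about 60 to 63 bpm, requires withdrawal but meets neither repeat-ECG trigger. The whole-millisecond band of 501 to 509 ms rests on the assumption that the period baseline is at most 450 ms. The practical effect falls mainly on findings first seen at 8 h or later.

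A reader might infer more than the documents support:

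- That such a participant would be dosed again or left unmonitored. Section 7.1.1 still requires withdrawal, and the provisions above remain in force.
- That the ECG analysis is affected. The SAP categories and the listing of values above 500 ms already use QTcF.
- That the event is likely. The documents give no QTcF or heart-rate distribution, so no likelihood can be stated.
- That all withdrawals without a trigger come from this wording. A rise above 60 ms with QTcF at or below 450 ms, such as 385 to 448 ms, also requires withdrawal without a trigger (465 pairs on the same grid). That follows from the 450 ms floor in (a) and is a separate matter.

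**What to change.** In the triplicate, single-ECG and continuous-monitoring paragraphs of Section 8.3.4, change trigger (b) to an absolute *QT or QTcF* value of at least 500 ms. In both exit rules and the single-ECG confirmation rule, compare whichever interval triggered (QT or QTcF) with its own threshold, and write QTcF where the single-ECG exit now says QTc. Leave trigger (a), Section 7.1.1 and Appendix 8 unchanged.

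Adding QTcF is preferable to replacing QT, because replacement would drop existing triggers at low heart rates. The change closes only the gap above 500 ms.

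The cost is a few extra repeat ECGs and a small wording amendment with IRB/EC approval (Section 10.1.1), which can be combined with the next amendment. It helps only Cohort 2 and the optional Cohort 3, because Section 4.1 records Cohort 1 as already discharged.
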